1 INTRODUCTION

This retrospective, non-interventional cohort study is designed to evaluate intra-operative, 6 months and 12 months safety and performance of the MINITAC[◇] Ti 2.0 Suture Anchors for extremities repair to meet post-market clinical follow-up requirements for extremities repair indications as outlined by the Notified Body (British Standards Institute (BSI)).

The purpose of the statistical analysis plan (SAP) is to lay out key elements including definitions and statistical methods for the planned analyses. As this is a descriptive study, all analyses will be of a descriptive nature, unless otherwise specified (i.e., no a priori statistical hypotheses will be tested). The final study report will detail all analyses, including minor modifications and any deviations from the planned analyses, and may describe analyses included in future abstracts and manuscripts. A regulatory submission is not planned.

The data source of the study is the medical charts of each participating subject to the extent that data are available. These will then serve as the input for the electronic Case Report Form (eCRF).

This SAP is based upon the following study documents:

- Study Protocol MINI.PMCF.2018.11, Version 3.0 (Aug. 20, 2019)
- eCRF, Version 3.0 (Jun. 21, 2019)

2 STUDY OBJECTIVES

2.1 Primary Objective(s)

The primary objective of this study is to assess safety and performance of the MINITAC[◇] Ti 2.0 Suture Anchor in extremities over a time period of 6 months after intervention.

2.2 Secondary Objective(s)

The secondary objective of this study is to assess safety and performance of the MINITAC[◇] Ti 2.0 Suture Anchor in extremities over a time period of 12 months after intervention.

3 INVESTIGATIONAL PLAN

3.1 Overall Study Design

This is a retrospective, multi-center, non-interventional cohort study to collect clinical data that will permit the evaluation of the safety and performance of the MINITAC[◇] Ti 2.0 Suture Anchor for indications in extremities. Up to 3 sites in Australia and the EU (European Union) will participate in the study enrolling a minimum of 30 subjects up to a maximum of 50 subjects into the study. Each enrolling site will enroll a minimum of 10 subjects.

Data from enrolled subjects will be recorded from the subject medical file on designated CRFs. Data will be collected retrospectively for different time points including preoperative, operative, 6 months postoperative and 12 months post-operative.

3.2 Identification of Analysis Populations

3.2.1 Full Analysis Set

The Full Analysis Set (FAS) includes all subjects enrolled in the study who had previously undergone arthroscopic repair using the MINITAC[◇] Ti 2.0 Suture Anchor. The FAS will be used for the analysis of all measures and endpoints.

3.3 Subgroup Analysis

Subgroup analyses will be performed to assess the consistency and robustness of the study product's performance mainly for the clinical success rate (%) of the MINITAC[◇] Ti 2.0 Suture Anchor in extremities at 6 months and 12 months postoperative with clinical success.

The following subgroups will be explored:

- Sex (male vs female)
- Age (≤ 40 , >40 to ≤ 60 vs > 60 years old)
- Race (white vs others)
- Ethnicity (Hispanic or Latino, Non-Hispanic or Latino)
- Primary diagnosis body system (foot, ankle, elbow, wrist vs hand)
- Body Mass Index (<25 , ≥ 25 to < 35 vs ≥ 35 kg/m²)

3.4 Interim Analysis

There is no interim analysis for this non-interventional study.

3.5 Study Endpoints

3.5.1 Primary Endpoint

The primary endpoint is the clinical success rate (%) of the MINITAC[◇] Ti 2.0 Suture Anchor in extremities at 6 months postoperative with clinical success defined as extremity repairs without signs of device failure and/or re-intervention as assessed by the surgeon. Device failure is also referred to as device malfunction which is failure to perform in accordance with the device's intended purpose when used in accordance with the instruction for use or the protocol.

3.5.2 Secondary Endpoints

The secondary endpoint is the clinical success rate (%) of the MINITAC[®] Ti 2.0 Suture Anchor in extremities at 12 months postoperative with clinical success defined as extremity repairs without signs of device failure and/or re-intervention as assessed by the surgeon. Again, device failure is also referred to as device malfunction which is failure to perform in accordance with the device's intended purpose when used in accordance with the instruction for use or the protocol.

3.5.3 Other Endpoints

Additional endpoints include surgeon reported outcomes as well as safety endpoints. There is expected to be a large volume of missing data associated with the surgeon reported outcomes.

3.5.3.1 Surgeon Reported Outcomes

Surgeon reported outcomes include specific data collected as standard of care and documented in the medical records. This will include:

- Range of Motion (ROM)
- Pain assessed by Visual Analogue Scale (VAS)
- Device Failure Criteria

A listing of device failure criteria will be collected for subjects that were assessed by the surgeon to have signs of device failure and/or re-intervention and therefore not meeting the definition of clinical success.

3.5.3.2 Safety Endpoints

Safety endpoints include the collection of the following events from the subjects' medical record:

- All adverse events (AEs) and complications occurring from the time of subject enrollment until study termination or study completion including intra-operative adverse events and complications
- Device related re-intervention
- Device deficiencies (DDs)

4 DATA SOURCE

The data source of the study is the medical charts of each participating subject to the extent it is available, which will serve as the input for the eCRF.

5 STATISTICAL METHODS

5.1 Data Quality Assurance

All tables, figures and data listings to be included in the report will be independently checked for consistency, integrity and in accordance with standard Parexel procedures for analysis and reporting.

5.2 General Presentation Considerations

As this study is of a descriptive nature, the analysis results will be reported using descriptive statistics.

Continuous data will be summarized in terms of the mean, standard deviation (SD), median, minimum, maximum and number of observations, unless otherwise stated. Continuous data that are expected to be skewed will be presented in terms of the maximum, upper quartile, median, lower quartile, minimum and number of observations. The minimum and maximum will be reported to the same number of decimal places as the raw data recorded in the database. The mean, median, lower quartile and upper quartile will be reported to one more decimal place than the raw data recorded in the database. The SD will be reported to two more decimal places than the raw data recorded in the database. In general, the maximum number of decimal places reported shall be four for any summary statistic.

Categorical data will be summarized in terms of the number of subjects providing data at the relevant time point (n), frequency counts and percentages. Percentages will be presented to one decimal place. Percentages will not be presented for zero counts. Percentages will be calculated using n as the denominator.

Given the small, convenience study sample, as well as the absence of *a priori* statistical hypotheses, no formal tests of statistical significance are planned, and as such, no p-values or statistical intervals will be calculated.

All report outputs will be produced using SAS[®] version 9.3 or a later version in a secure and validated environment. All report outputs will be provided to the Sponsor as individual .rtf files and as a consolidated .pdf document.

5.3 Statistical methods

5.3.1 General Analysis Definitions

Screening / Enrollment: For screening, only information available in the medical records will be reviewed. When all inclusion criteria and none of the exclusion criteria have been met for a subject and the informed consent process has been completed or a waiver of consent has been granted by the HREC/EC, the subject will be considered enrolled.

Baseline: Unless specified otherwise, the last non-missing value before study product installation/operation collected at the screening visit is considered as the baseline value.

Study Day:

Study Day = assessment date – study product installation/operation date + 1 for assessments post operation;

Study Day = assessment date – study product installation/operation date for assessments prior to operation;

All durations are calculated as the stop date minus the start date +1 unless otherwise specified.

End of Study: Due to the retrospective design of the study, end of the study is defined as the date when the last subject is documented on CRFs.

5.3.2 Analysis of the Primary Endpoint

The proportion of subjects with clinical success at 6 months post operation (182 days + 30 / -150 days) will be summarized with a frequency and percentage. Clinical success is achieved only if all of the following are true for a patient (as indicated by the items in the impact status form in the study case report form):

- Did not experience any inflammation;
- Did not have any device related AEs;
- Did not have any device deficiencies;
- Did not experience any device failure (malfunction);
- Did not have any signs of repair failure, and;
- Did not undergo any re-intervention.

Subgroup (defined in section 3.3) corresponding proportions will be presented in tabular form. All analyses will be carried out using the FAS.

In addition, the primary endpoint will also be estimated for +/- 3 months (3-9 month window) as per standard of care.

Incidence rates of the post-operative device failure and/or device related re-intervention at 6 months will be estimated. Specifically, the following will be summarized and estimated:

- The number of patients at risk of an event;
- The number of patients with events;
- The number of events;
- Total person-months;
- Crude rate/person-months;
- Estimated rate.

Person-months are months for each patient between baseline and 6 months included in the FAS. The estimated rate will be derived using Poisson regression with an offset as (the log of) the duration at risk for each patient.

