## 8.2 STUDY ENDPOINTS

### 8.2.1 Primary Endpoint

Clinical success rate (%) of the MINITAC◇ Ti 2.0 Suture Anchor in extremities at 6 months post-operative with clinical success defined as extremity repairs without signs of device failure and/or re-intervention as assessed by the surgeon.

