### 8.2.3 Other Endpoints

Additional endpoints include surgeon reported outcomes as well as safety endpoints.

Surgeon reported outcomes include specific data collected as standard of care and documented in the medical records. This might include but is not limited to the following:

- Range of Motion (ROM)
- Pain assessed by Visual Analogue Scale (VAS)

Surgeon reported outcomes are optional and will be definitively specified in collaboration with the Investigators once sites have been identified for the conduct of the study.

In addition, a listing of device failure criteria will be collected for subjects that were assessed by the surgeon to have signs of device failure and/or re-intervention and therefore not meeting the definition of clinical success.

Safety endpoints include the collection of the following events from the subjects' medical record:

Study Protocol—Device	
Safety and Performance of MINITAC® Ti 2.0 Suture Anchor in Extremities	Number: MINI.PMCF.2018.11
	Version: 3.0, 20Aug19
	Page: Page 23 of 56

- All adverse events (AEs) and complications occurring from the time of subject enrollment until study termination or study completion including intra-operative adverse events and complications.
- Device related re-intervention.
- Device Deficiencies.

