## **10. STATISTICAL DESIGN**

A SAP will be written and finalized prior to database lock. The SAP will contain more specific details of the statistical analyses that will be carried out as well as provide information on any changes or deviations from the projected analyses in this protocol. The Clinical Study Report will also highlight changes made to the analyses specified in the protocol.

Study Protocol—Device	
Safety and Performance of MINITAC◇ Ti 2.0 Suture Anchor in Extremities	Number: MINI.PMCF.2018.11
	Version: 3.0, 20Aug19
	Page: Page 28 of 56

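### SAP 5.3.2 adds three criteria to the primary endpoint that the protocol definition does not contain, and SAP 5.8 does not declare the change

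*SAP*

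**What the plan says.** Protocol 8.2.1 gives the 6-month primary endpoint as a success rate, with "clinical success defined as extremity repairs without signs of device failure and/or re-intervention as assessed by the surgeon". Protocol 9.2 repeats the definition, and SAP 3.5.1 restates it and adds that "Device failure is also referred to as device malfunction".

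SAP 5.3.2 then gives the rule that will be programmed: "Clinical success is achieved only if all of the following are true for a patient". Six items follow. Three concern device failure (malfunction), signs of repair failure, and re-intervention. The other three are "Did not experience any inflammation", the absence of device related AEs, and "Did not have any device deficiencies".

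Elsewhere these other items are handled differently. Protocol 8.2.3 has a separate list that opens "Safety endpoints include the collection of the following events"; AEs and device deficiencies are on it, and SAP 3.5.3.2 repeats it. SAP 3.5.3.1 collects device failure criteria for subjects judged to "have signs of device failure and/or re-intervention and therefore not meeting the definition of clinical success".

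Protocol section 10 says the SAP will "provide information on any changes or deviations from the projected analyses in this protocol". SAP 5.8 lists four changes: no tests or confidence intervals, a single analysis set, incidence rates in place of Kaplan-Meier event rates, and an added 3-9 month window. SAP 5.3.4 plans no sensitivity analyses.

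**The concern.** The SAP contains two definitions of its primary endpoint. Under SAP 3.5.1, a sound repair with transient inflammation, or with a labelling deficiency noted at surgery, can be a success. Under SAP 5.3.2 it is a failure whatever the surgeon concluded. The reported figure would carry the protocol endpoint's name while measuring a mixture of performance and safety.

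The change is also hard to see. It is missing from the section where the protocol says changes will be reported, and no sensitivity analysis shows the result under the protocol definition. A subject who fails only on an added item counts against the device in SAP 5.3.2 but falls outside the SAP 3.5.3.1 listing, which would explain failures only in terms of device failure or re-intervention. SAP 5.3.3 gives no rule of its own for 12 months, so the same ambiguity probably extends to the secondary endpoint.

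**Working it through.** **1. The six items against the definition**

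| SAP 5.3.2 requires none of | In Protocol 8.2.1 and SAP 3.5.1? | Where else it appears |
|---|---|---|
| Device failure (malfunction) | Yes | – |
| Re-intervention | Yes | – |
| Signs of repair failure | Not by name | Part of the clinical success assessment in Protocol Table 9.1-1 and 9.1.3 |
| Inflammation | No | Not tied to clinical success anywhere else |
| Device related AEs | No | AEs are a safety endpoint (Protocol 8.2.3, SAP 3.5.3.2) |
| Device deficiencies | No | Safety endpoint; Protocol 12.1.6 extends it to use errors and inadequate labelling |

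The protocol supports three items and not the other three. The added items cannot simply be read as device failure. SAP 3.5.1 equates device failure with malfunction, and SAP 5.3.2 gives malfunction its own line.

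**2. Direction.** Every subject who meets the six-item rule also meets the three supported items; the reverse does not hold. With the same subjects in the denominator and the same judgement of the three shared items, the SAP 5.3.2 rate is equal to or below the protocol rate.

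**3. The plan's own figures.** Inputs: success rate 95% and precision ±10 points (Protocol section 11, SAP 5.7), exact Clopper-Pearson 95% interval (Protocol 10.4.1), n = 30 and n = 50. The stated probabilities are those of an interval no wider than 20 points.

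- n = 30: the width is 0.171 at 29/30 and 0.213 at 28/30, so at least 29 successes are needed. P(X ≥ 29) = 0.95^30 + 30 × 0.95^29 × 0.05 = 0.2146 + 0.3389 = 0.5535 (stated 55.4%).
- n = 50: the width is 0.198 at 44/50 and 0.209 at 43/50, so at least 44 are needed. P(X ≥ 44) = 0.9882 (stated 98.8%).

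Both figures reproduce.

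**4. Illustrative size.** The documents give no frequency for the added items. Let f be the assumed share of protocol-defined successes that fail only on an added item. Then:

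- SAP 5.3.2 success rate: p = 0.95 × (1 − f)
- expected number of subjects reclassified: n × 0.95 × f
- precision probability: the binomial tails of step 3, evaluated at p

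| f (assumed) | p | Reclassified, n = 30 | Reclassified, n = 50 | P(width ≤ 20 points), n = 30 | P(width ≤ 20 points), n = 50 |
|---|---|---|---|---|---|
| 0 | 95.0% | 0 | 0 | 55.4% | 98.8% |
| 2% | 93.1% | 0.57 | 0.95 | 37.7% | 94.5% |
| 5% | 90.3% | 1.43 | 2.38 | 19.5% | 78.9% |
| 10% | 85.5% | 2.85 | 4.75 | 5.5% | 39.9% |

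One reclassified subject moves the reported rate by 1/30 = 3.3 points or 1/50 = 2.0 points. The last two columns bear only on the sample-size justification, because the SAP no longer computes the interval.

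**5. What the other planned outputs show.** The incidence rates (SAP 5.3.2, 5.3.3) and the Kaplan-Meier analysis (SAP 5.3.3) count device failure or device related re-intervention. That is close to the protocol endpoint but narrower, because Protocol 8.2.1 does not limit re-intervention to device related cases. The protocol itself is inconsistent here: Table 9.1-1 and 9.1.3 do apply that limit.

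**The case against.** The best defence is that SAP 5.3.2 only puts the endpoint into operation. Protocol 9.2 has the surgeon record the criteria used on a CRF, Protocol 9.1.3 assesses success by reviewing implant status, and SAP 5.3.2 takes its items from a CRF form that is not available here. The items also overlap: Protocol 12.1.6 counts malfunctions among device deficiencies, so a separate line does not prove a separate concept. The definition speaks of signs of device failure, which can be read more widely than malfunction. In addition, repair failure is accepted here although Protocol 8.2.1 does not name it.

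Part of this stands. The list may well have been meant to operationalise the form. But Protocol 9.2 covers only the surgeon's criteria for device failure and re-intervention, whereas SAP 5.3.2 makes the added items automatic failures. Device deficiency includes malfunction but goes well beyond it. Repair failure has support in the protocol schedule as part of assessing clinical success, and the three added items have none. Whatever the form says, SAP 3.5.1 and 5.3.2 disagree.

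Two limits are fair. SAP 5.2 uses subjects with data as the denominator, SAP 5.6 imputes nothing, and neither says how a subject with one missing item is counted. The equal-or-lower statement therefore needs a common denominator. The carry-over to 12 months is an inference from the silence of SAP 5.3.3; SAP 3.5.2 restates the protocol definition.

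It can also be said that the study is descriptive, that a stricter rule works against the device, and that the by-subject success listing, the implant status summary and the re-intervention and deficiency outputs would let a reader largely reconstruct the protocol result. This limits the harm. It does not supply a table of the protocol-defined proportion or make the change a declared one.

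**Conclusion.** The point holds, and it rests on the text rather than on a calculation. SAP 5.3.2 changes what the primary success rate measures, contradicts SAP 3.5.1, and is not declared in SAP 5.8 as Protocol section 10 requires. It must be fixed, because the reported primary rate depends on which section is followed.

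The size cannot be known from the documents. What is certain is 3.3 points per reclassified subject at n = 30 and 2.0 points at n = 50. Under the assumed 2% to 10% range, the expected rate falls from 95% to between 93.1% and 85.5%, while SAP 5.7 still carries 95%. Confidence in the contradiction is high; the magnitudes are illustrations.

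**What to change.** In SAP 5.3.2 and 5.3.3, derive the primary and secondary endpoints from the surgeon-assessed protocol definition: device failure, including signs of repair failure as in the protocol schedule, and re-intervention. Report the six-item composite as a named supplementary result and declare it in SAP 5.8. If the sponsor does intend any added item to count as device failure, say which in SAP 3.5.1 and 5.8.

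Separately, reconcile the scope of re-intervention between Protocol 8.2.1 and Protocol Table 9.1-1 and 9.1.3. State how the narrower event in the incidence and Kaplan-Meier analyses relates to the endpoint.

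The cost is SAP wording, one line in SAP 5.8 and one extra table, plus the protocol clarification on re-intervention. SAP 5.3.2 indicates that the items are already on the case report form, so no new data are needed.

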5.3.3 Analysis of the Secondary Endpoint

The proportion of subjects with clinical success at 12 months post operation (365 days + 30 / - 150 days) will be summarized with a frequency and percentage. . As with the primary endpoint, subgroup (defined in section 3.3) corresponding proportions will be presented in tabular form. .

Incidence rates of the post-operative device failure and/or device related re-intervention at 12 months will be estimated as described above for the analysis of the primary endpoint.

Time to the first case of postoperative device failure and/or device-related re-intervention from operation date will be analyzed using the Kaplan-Meier method to estimate median time and related 25th and 75th percentiles. Patients without postoperative device failure or device related re-intervention will be censored at the latest date of assessment based on CRF data or date of death, whichever is earlier.

A by-subject listing of clinical success status will be provided for all subjects in the safety population. The listing will include subject identifier, date of 6-month visit, date of 12-months visit, clinical success status at 6-month visit or 12-month visit, date of device failure, description of failure, date of re-intervention, reason of re-intervention, and other information.

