**9.1.4 Retrospective chart review at 12 Months (365 days) Post-Operative (+ 30 days / -150)**

Given the retrospective study design, data will be collected from the medical chart to the extent it is available.

- |   |
|---|
| 
1. Collect the following retrospective data, to the extent it is available, from the subject's medical chart and complete the associated CRFs:
 
 
• Review study implant status 12 months post-operative for device related re-interventions and/or repair failure and assess clinical success.
 
• Obtain surgeon reported outcomes as defined in section 8.2.3 to the extent available at the 12 months follow-up.
 
• Collect Adverse Events and Device Deficiencies occurring from 6 months until 12 months follow-up.
 
• Collect concomitant medications or therapies.
 
 |
|---|

Study Protocol—Device	
Safety and Performance of MINITAC® Ti 2.0 Suture Anchor in Extremities	Number: MINI.PMCF.2018.11
	Version: 3.0, 20Aug19
	Page: Page 27 of 56

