5.3.4 Sensitivity Analyses

No sensitivity analyses are planned.

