5.6 Handling of Missing and Uninterpretable Data

Missing data will not be imputed, and the data will be analyzed as they were entered in the study database.

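### SAP 5.3.3 does not carry an early failure forward, so a failed subject with no 12-month record can drop out of the 12-month success rate

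*SAP*

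**What the plan says.** SAP 5.3.3 defines the analysis as "The proportion of subjects with clinical success at 12 months post operation", with a window of 30 days after and 150 days before day 365. It does not restate the success criteria, give a look-back period, or say how a failure before the window is scored.

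The denominator comes from SAP 5.2: "Categorical data will be summarized in terms of the number of subjects providing data at the relevant time point (n), frequency counts and percentages", and then "Percentages will be calculated using n as the denominator". SAP 5.6 adds: "Missing data will not be imputed, and the data will be analyzed as they were entered in the study database". SAP 5.3.4 is one line: "No sensitivity analyses are planned". SAP 3.2.1, on the other hand, assigns the FAS, meaning all enrolled subjects who had the repair, to every endpoint, and 5.3.2 says the same for the primary analysis.

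The six components of success appear only in SAP 5.3.2, under the primary endpoint, and are read from a status form. They are inflammation, device-related adverse events, device deficiencies, device failure, signs of repair failure, and re-intervention. Success requires the absence of all six.

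Protocol 9.1.4 gives the 12-month chart review two relevant tasks. The first has no start date: "Review study implant status 12 months post-operative for device related re-interventions and/or repair failure and assess clinical success". The second covers a limited interval: "Collect Adverse Events and Device Deficiencies occurring from 6 months until 12 months follow-up". Data are taken as far as the chart has them. There are no prospective visits (Protocol 7.5), and follow-up depends on the site's standard of care (Protocol 7.7).

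**The concern.** A device failure or a re-intervention, once it has happened, does not become unknown because the patient has no later clinic entry. Under the denominator rule, however, it can vanish from the 12-month percentage. The 12-month rate could then exceed the 6-month rate because known failures were removed, not because repairs lasted. The study is meant to give the Notified Body evidence on safety and performance, and a 12-month figure of 100% could be reported while the charts document failures.

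The second question is look-back. Device-related adverse events and device deficiencies are two of the six components, and the 12-month review collects them for months 6 to 12 only. If a programmer derived 12-month success from that review alone, a subject with a device deficiency in month 2 could pass those two components.

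**Working it through.** **The plan's own figures.** SAP 5.7 gives a 55.4% probability of the target precision at n = 30 and 98.8% at n = 50, for a true success rate of 95%. Both reproduce as the exact binomial probability that the Clopper-Pearson 95% interval has a half-width of at most 0.10.
- n = 30: the half-width is 0.1063 at 28 successes and 0.0857 at 29, so at least 29 are needed. P(X ≥ 29) = 0.95^30 + 30 × 0.05 × 0.95^29 = 0.2146 + 0.3389 = 0.5535.
- n = 50: the half-width is 0.1046 at 43 and 0.0989 at 44. P(X ≥ 44) = 0.9882.

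These figures concern precision only and do not depend on how early failures are scored at 12 months.

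**Window.** 365 − 150 = day 215; 365 + 30 = day 395.

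**Early failures without a 12-month record.** Let N be the subjects enrolled, E the failures before day 215 with no in-window record, and L the other failures. Suppose every event-free subject has a record.
- Cumulative rate: (N − E − L)/N.
- Rate under SAP 5.2 and 5.6: (N − E − L)/(N − E).

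The documents give neither failure timing nor 12-month attrition. The counts below are assumptions near the 95% planning rate.

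| N | E | L | Cumulative | As planned |
|---|---|---|---|---|
| 50 | 3 | 0 | 47/50 = 94.0% | 47/47 = 100% |
| 50 | 2 | 1 | 47/50 = 94.0% | 47/48 = 97.9% |
| 30 | 2 | 0 | 28/30 = 93.3% | 28/28 = 100% |
| 30 | 1 | 1 | 28/30 = 93.3% | 28/29 = 96.6% |

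The overstatement is about 3 to 7 percentage points. For scale only, the exact lower 95% limits would be 0.025^(1/47) = 92.5% for 47/47 against 83.5% for 47/50, and 0.025^(1/28) = 87.7% for 28/28 against 77.9% for 28/30. SAP 5.2 and 5.8 drop intervals, so these would not be reported.

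**The reverse case.** Keep all F failures and let a fraction m of event-free subjects lack a record. The rate is w/(w + F), with w = (N − F)(1 − m), rounded.
- N = 30, F = 2: m = 20% gives 22/24 = 91.7%; m = 60% gives 11/13 = 84.6%. The full-cohort value is 93.3%.
- N = 50, F = 3: m = 20% gives 38/41 = 92.7%; m = 60% gives 19/22 = 86.4%. The full-cohort value is 94.0%.

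If failed and event-free subjects lack records in equal proportion, the factor (1 − m) cancels and the rate is unchanged. The sign therefore depends on who is missing.

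**Look-back.** Protocol 9.1.2, 9.1.3 and 9.1.4 collect adverse events and deficiencies in consecutive periods: to discharge, discharge to 6 months, and 6 to 12 months. Taken together they cover the whole course. No text says whether 12-month success uses all three periods or only the last.

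**The case against.** The strongest reply is that the plan, read sensibly, is already cumulative. The criteria in SAP 5.3.2 are framed per patient as the absence of *any* event, and the implant-status review in Protocol 9.1.4 has no start date. Splitting collection into periods avoids double entry; it is not a scoring rule. All subjects are more than 12 months post-operative, the 12-month visit is itself a chart review, and a re-operation in month 3 is in the chart for that review to find. The current schedule does not end follow-up at failure. SAP 3.2.1 names the FAS for everything. SAP 5.3.3 also plans incidence rates, a Kaplan-Meier analysis from the operation date, and a by-subject listing with failure and re-intervention dates. The endpoint is secondary and descriptive.

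Much of this stands. A reader might infer that the plan scores early failures as 12-month successes. The documents do not say so: for re-intervention and repair failure the text leans towards a cumulative reading, and for adverse events and deficiencies it is silent. A reader might also infer that the endpoint is biased in the device's favour. That would need to be known from failure timing and attrition, which the documents do not give, and the reverse case above shows that the rate can also be too low.

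The denominator point survives. Naming the FAS does not override a specific instruction to divide by those with data, and a cumulative criterion does not help a subject who has no record at the time point. Nor do the other outputs repair the percentage. The incidence rates and the Kaplan-Meier analysis cover only device failure and device-related re-intervention, not inflammation, other device-related adverse events or deficiencies. Kaplan-Meier is planned for the quartiles of time, which would probably not be reached if about 5% of subjects fail, and SAP 5.8 rules it out for the event rate. The listing shows the failures but leaves the headline figure as it is.

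**Conclusion.** The concern holds in a limited form. Followed literally, SAP 5.2, 5.6 and 5.3.3 allow a documented early failure without a day 215 to 395 record to leave the 12-month success rate. The rate can then be about 3 to 7 points too high at the study's sample sizes, assuming 2 failures in 30 or 3 in 50, at least one of them early and unrecorded in the window, and complete records for event-free subjects. If event-free subjects are the ones without records, the rate is too low instead, by roughly 1 to 9 points for 20% to 60% missing. The documents do not show which will dominate. The look-back for device-related adverse events and device deficiencies is an ambiguity to be settled, not an error in a stated rule. The point is worth settling before database lock, but it concerns a descriptive secondary endpoint.

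**What to change.** 1. State in SAP 5.3.2 and 5.3.3 that success is cumulative from the operation for device failure, repair failure, re-intervention, device-related adverse events and device deficiencies, combining all collection periods. A documented failure is a non-success at that time point and every later one, with or without an in-window record.
2. State whether inflammation is judged cumulatively or at the visit. This is a choice of what the endpoint measures, and the documents do not settle it.
3. Treat event-free subjects without 12-month data explicitly. Keeping every failure while still dropping these subjects would create the opposite bias. Report the rate on the FAS with best-case and worst-case bounds for them, alongside the observed-data rate. A 12-month Kaplan-Meier estimate censoring them at last assessment is an alternative, but SAP 5.8 would then need amending.
4. Reconcile SAP 3.2.1 with 5.2 on the denominator.

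The cost is a few sentences, a little more analysis and a possibly lower 12-month rate. The bounds may be wide: with 3 failures in 50 and 9 event-free subjects unrecorded, they run from 38/50 = 76.0% to 47/50 = 94.0%. Dates for failure, re-intervention and adverse events, and time to deficiency, are already planned outputs (SAP 5.3.3, 5.3.6.2, 5.3.6.4). Neither document shows a date for inflammation or signs of repair failure, so the case report form should be checked for those two.
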